4.7.1.2 Recording of adverse events

AEs will be recorded in the CRF from consent (Visit 1) until Visit 5. Any AEs remaining unresolved at Visit 5 should be recorded as "ongoing" in the CRF. Where appropriate, these should be followed as long as medically indicated but without further recording in the CRF. AstraZeneca retains the right to request additional information judged necessary, for any patient with ongoing AE(s)/SAE(s) at the end of the study.

The following variables will be recorded for each AE: AE description, start and stop date, intensity, action taken, outcome, investigator's causality rating (yes or no), and whether the AE meets criteria for a SAE or not.

The following levels of intensity will be recorded

- mild (awareness of sign or symptom, but easily tolerated)
- moderate (discomfort sufficient to cause interference with normal activities)
- severe (incapacitating, with inability to perform normal activities)

It is important to distinguish between serious and severe AEs. Severity is a measure of intensity whereas seriousness is defined by the criteria in Section 4.7.1.1. An AE of severe intensity need not necessarily be considered serious. For example, nausea that persists for

several hours may be considered severe nausea, but not a SAE. On the other hand, a stroke that results in only a limited degree of disability may be considered a mild stroke but would be a SAE.

AEs will be collected on an ongoing basis All AEs spontaneously reported by the subject or reported in response to open questions from the study personnel: "Have you had any health problems since the previous visit?" or "Have you had any health problems since you were last asked" or revealed by observation will be collected and recorded in the CRF. The first AE questioning will occur at Visit 2.

Signs and symptoms present at Visit 1 will be recorded as 'ongoing pre-dose'. When the severity or seriousness of any pre-dose signs or symptoms changes this will be recorded as a new AE.

AEs and any abnormalities in laboratory tests, vital signs or physical examination of clinical relevance will be followed up until resolution or no further improvement is expected in the opinion of the Investigator. Patients who drop out during the study for reasons other than discontinuation of study drug will be followed up for the planned duration of the study. Abnormalities in laboratory tests and vital signs will be recorded and reported on the laboratory reports and CRFs respectively. Abnormalities in these variables will be identified, analysed and reported in the Clinical Study Report. Laboratory results that constitute a SAE or lead to discontinuation of the study drug will be recorded and reported as an AE. In addition, any abnormality in laboratory tests which meets the stopping criteria as described in Section 3.3.5, will be recorded as an AE.

Should an overdose (accidental or deliberate) occur, it must be reported in accordance with the procedures described in Section 9.3, Procedures in case of overdose, regardless of whether the overdose was associated with any symptom or not. All symptoms associated with the overdose should be reported as AEs.

Should a pregnancy occur, it must be reported in accordance with the procedures described in Section 9.4 - Procedures in case of pregnancy. Pregnancy in itself is not regarded as an AE unless there is a suspicion that an investigational product may have interfered with the effectiveness of a contraceptive medication.

If patients annotate their diary card or questionnaires with comments, these will be reviewed by the study centre staff in consultation with the patient, in case the annotation represents an AE.

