- 2. To investigate the clinical effects of AZD9668 by using the BronkoTest[©] diary card.
- 3. To investigate the effect of AZD9668 on markers of tissue degradation (including but not limited to urine and plasma desmosine, and sputum hydroxyproline). These exploratory biomarkers may be reported separately, not as part of the main Clinical study report.
- 4. To collect samples for possible retrospective pharmacogenetics analysis to investigate the influence of genotype on exposure (ADME), pharmacodynamic response including inter-individual biomarker response variability, tolerability and safety where appropriate. The results of the pharmacogenetic tests may be reported separately, not as part of the main Clinical study report.

Study design

This study is a randomised, double-blind, placebo-controlled, parallel-group, single-centre study to evaluate the tolerability and pharmacokinetics of AZD9668 administered for 14 days, in patients with moderate to severe COPD (GOLD stages II and III). 18 patients will be randomly assigned to receive either AZD9668 or matching placebo orally (in a ratio of 2 active: 1 placebo).

The pharmacogenetic research aspects of the study are not mandatory for the individual patients. Ethical approval is requested for these research components, in addition to, and separate from, approval for the main study.

Target patient population

Male and postmenopausal or surgically sterile female patients with moderate to severe COPD (GOLD stages II and III), aged between 40 to 80 years. Patients will be smokers or exsmokers, with a history of >10 pack-years, post-bronchodilator FEV₁ 30–80% predicted and FEV₁/FVC ratio < 70%.

Investigational product, dosage and mode of administration

AZD9668 will be administered as 30 mg tablets. On Day 1 patients will receive a single morning dose of 60 mg of AZD9668 (or matching placebo) for single dose PK. This will be

followed by daily doses of 60 mg b.i.d (twice daily, 12 hours apart) on Days 2 to 13 and finally a single morning dose of 60 mg on Day 14 for steady state PK.

Comparator, dosage and mode of administration

Matching placebo tablets will be given according to the same regimen as the IMP.

Duration of treatment

14 days.

Outcome variables

Primary outcome variables

- Tolerability:

Adverse events, vital signs, ECG, lung functions, haematology, clinical chemistry, and urinalysis.

- Pharmacokinetic:

- AZD9668 plasma and urine concentrations

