1. INTRODUCTION

1.1 Background

Chronic obstructive pulmonary disease (COPD) is the fourth leading cause of morbidity and mortality in the US (US Department of Health and Human Services 1998) and worldwide is projected to rank fifth in burden of disease in 2020 (Lopez 1998). The prevalence of physiologically defined COPD in adults, aged 40 years or over, is around 9-10% (Halbert 2006). A significant proportion of these patients suffer from severe disability, and this subset of patients contributes largely to the health care costs of COPD (Rutten van Molken 1999).

COPD is a chronic lung disease, characterized by airflow limitation that is not fully reversible, and this is associated with an abnormal chronic inflammatory response in the respiratory system to noxious particles or gases (GOLD 2005). Currently, the mainstay of treatment of airflow limitation is bronchodilators. Despite a prominent inflammatory response in the airways in COPD, in contrast to asthma, anti-inflammatory therapy with corticosteroids is relatively ineffective. Therefore, there is a need to explore the possibilities of developing other therapies for COPD.

Neutrophil elastase (NE) is a serine protease found in high levels in neutrophils. NE is able to degrade extracellular matrix and proteins leading to long-term destruction of the lung parenchyma. Inhibition of neutrophil elastase has the potential to inhibit this proteolytic destruction raising the possibility of disease modification. If, as predicted from in vivo studies, NE inhibition can affect not only lung destruction but also epithelial metaplasia, goblet cell hyperplasia and the loss of cilia caused by exposure to cigarette smoke, as well as infiltration of inflammatory cells, shorter-term symptomatic benefits are also possible with this approach.

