4.7.1 Adverse events

4.7.1.1 Definitions

The definitions of adverse events (AEs), serious adverse events (SAEs) and other significant adverse events (OAEs) are given below. It is of the utmost importance that all staff involved in the study are familiar with the content of this section. The principal investigator is responsible for ensuring this.

Adverse event

An adverse event is the development of an undesirable medical condition or the deterioration of a pre-existing medical condition following or during exposure to a pharmaceutical product, whether or not considered causally related to the product. An undesirable medical condition can be symptoms (eg, nausea, chest pain), signs (eg, tachycardia, enlarged liver) or the abnormal results of an investigation (eg, laboratory findings, electrocardiogram). In clinical studies, an AE can include an undesirable medical condition occurring at any time, including run-in or washout periods, even if no study treatment has been administered.

Serious adverse event

A serious adverse event is an AE occurring during any study phase (ie, run-in, treatment, washout, follow-up), and at any dose of the investigational product, comparator or placebo, that fulfils one or more of the following criteria:

- Results in death
- Is immediately life-threatening
- Requires in-patient hospitalisation or prolongation of existing hospitalisation
- Results in persistent or significant disability or incapacity
- Is a congenital abnormality or birth defect

• Is an important medical event that may jeopardise the patient or may require medical intervention to prevent one of the outcomes listed above.

The causality of SAEs (ie, their relationship to study treatment) will be assessed by the investigator(s), who in completing the relevant case report form must answer "yes" or "no" to the question "Do you consider that there is a reasonable possibility that the event may have been caused by any of the following – study medication – other medication?" For further guidance on the definition of a SAE and a guide to the interpretation of the causality question, see Appendix B to the Clinical Study Protocol.

Note that SAEs that could be associated with any study procedure should also be reported. For such events the causal relationship is implied as "yes".

Other Significant Adverse Events (OAE)

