6.4.4 Safety analysis

Examination of the following safety variables will address the primary objective to investigate the tolerability of 14 days' treatment with AZD9668. No formal hypotheses will be associated with these variables, although informal comparisons will be made between treatment groups to determine whether there appears to be any treatment-related effects: adverse events, vital signs, 12-lead ECG (overall evaluation), lung function, sputum bacteriology, safety lab data (clinical chemistry, haematology, urinalysis), physical examination and concomitant medication.

Adverse events will be analysed by means of descriptive statistics and qualitative analysis. AEs will be listed for each patient and summarised by System Organ Class and preferred term assigned to event by using MedDRA 10.0.

Concomitant medications will be classified according to the AZDD Drug Dictionary, the ATC system and the CPMP route of administration dictionary. All concomitant medications reported at entry and recorded during the study will be summarised and listed.

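### The AE recording rule in Protocol Section 4.7.1.2 covers a change of a pre-dose symptom in either direction, whereas the AE definition in Section 4.7.1.1 covers only worsening

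*Protocol*

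**What the plan says.** Section 4.7.1.1 of the Protocol defines an AE as either a new undesirable condition or "the deterioration of a pre-existing medical condition following or during exposure to a pharmaceutical product". It stresses the standing of that text: "It is of the utmost importance that all staff involved in the study are familiar with the content of this section".

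Section 4.7.1.2 turns to the CRF. Baseline findings are flagged first: "Signs and symptoms present at Visit 1 will be recorded as 'ongoing pre-dose". The next sentence is the recording rule: "When the severity or seriousness of any pre-dose signs or symptoms changes this will be recorded as a new AE".

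AEs head the tolerability list among the primary outcome variables in the synopsis: "Adverse events, vital signs, ECG, lung functions, haematology, clinical chemistry, and urinalysis". Section 6.4.4 describes their reporting: "AEs will be listed for each patient and summarised by System Organ Class and preferred term". It adds that "informal comparisons will be made between treatment groups to determine whether there appears to be any treatment-related effects".

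**The concern.** The definition and the recording rule disagree on one point, direction. The definition admits only worsening of an existing condition. The rule admits any change of severity or seriousness and says that a new AE will be recorded.

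The population makes this more than a drafting nicety. All patients have moderate to severe COPD, so many are likely to have breathlessness, cough or sputum at Visit 1, and the rule then applies to those symptoms. The patients keep a daily symptom diary, and site staff review any comments they write in it as possible AEs (Section 4.7.1.2), so changes in baseline symptoms may well come to the site's notice.

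What is at stake is the meaning of an AE entry in a primary tolerability outcome. If some entries are improvements, the tables by arm mix relief with harm. Each AE also carries a yes/no causality rating, so an improvement entered this way could be rated as caused by study drug.

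**Working it through.** No arithmetic in the plan bears on this point, so the check sets the texts side by side and follows an entry through to the tables.

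**Step 1: apply both texts to one example.** Take a patient with moderate cough at Visit 1.

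| Later state | AE under Section 4.7.1.1? | New AE under Section 4.7.1.2? |
|---|---|---|
| Severe | Yes, deterioration | Yes |
| Moderate | No | No |
| Mild | No, improvement | Yes, severity has changed |
| Mild, then moderate again | Unclear: worse than the day before, no worse than at Visit 1 | Yes, on a literal reading, at each step |

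The texts agree on a worsening and on a stable symptom. They part on improvement, and on the return from improvement.

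**Step 2: look for a rule of precedence.** Section 4.7.1.2 does not refer back to the deterioration limit when it states the rule, and neither section says which governs. Amendment 01, as far as it is shown, changes eligibility, discontinuation and stopping criteria and the references, and leaves both sections alone.

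**Step 3: see what the CRF captures.** For each AE, Section 4.7.1.2 lists what the event was, when it began and ended, its intensity, the action taken, its outcome, the investigator's causality rating and whether it is serious. No item gives the direction of change or links the new entry to the pre-dose one. A mild cough entered after improvement looks the same as a new mild cough.

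**Step 4: see what the summary shows.** Section 6.4.4 summarises by System Organ Class and preferred term. Both kinds of mild cough fall under the same term. The patient listing also planned there could reveal the difference, if a reader compares the new entry with the pre-dose one.

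**Step 5: size.** Section 3.1 plans 18 patients at 2:1, which gives 18 × 2/3 = 12 active (the number stated in Section 3.2.1) and 18 × 1/3 = 6 placebo. If the summaries count patients, one patient who appears under a term only because of an improvement entry moves that term's incidence by 1/12 = 8.3 percentage points on active or 1/6 = 16.7 on placebo. That is the weight of a single patient. The number of patients affected cannot be derived: the protocol gives no rate of symptom change, no count of baseline symptoms per patient and no indication of how sites would read the rule.

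**The case against.** The strongest reply is that Section 4.7.1.2 governs how AEs are recorded and does not redefine them. On that view an improvement cannot be a new AE, because it is not an AE at all, and staff are told to know the definition. The pairing of severity with seriousness also suggests that the author meant worsening, since Section 4.7.1.3 discusses only a non-serious event becoming serious. And AEs are gathered by open questions about health problems, by spontaneous report and by observation; no step re-grades every baseline symptom at each visit. Relief of a cough is unlikely to be offered in answer to such a question.

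Much of this stands. It shows that the intended reading is probably the narrow one and that many improvements would never be entered. It does not remove the contradiction: the rule is a specific, mandatory instruction to whoever completes the CRF, and its wording is wider than the definition.

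A reader might infer more than the documents support:

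- *That improvement will be counted as harm.* This follows only if the site applies the rule literally. A site working from Section 4.7.1.1 would not enter it.
- *That active treatment will look worse because it relieves symptoms.* Section 1.1 does say that "shorter-term symptomatic benefits are also possible with this approach", but the statement is conditional on predictions from in vivo studies and concerns inhibition of neutrophil elastase in general. Section 3.2.2 expects no individual benefit for these patients. Nothing predicts relief within 14 days large enough to tilt the AE counts.
- *That the AE comparison decides whether longer studies proceed.* The study is a preliminary to them, but no go/no-go rule is tied to AE counts.
- *That Visit 1 is the wrong reference and Day 1 should replace it.* Recording from consent is deliberate, and Section 4.7.1.1 expressly includes events in run-in before any study treatment. A Day 1 reference could lose worsening that the protocol means to capture.

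**Conclusion.** The point holds as an internal inconsistency: Section 4.7.1.2 is wider than the definition it serves, and on a literal reading it puts improvements into a primary tolerability outcome. The possible effect is misclassified entries in a descriptive comparison of 12 active and 6 placebo patients. The number of such entries cannot be estimated from the protocol and could be zero.

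The conclusion assumes that at least some site staff would follow the recording sentence as it stands. No sample size, alpha or power is touched: Section 6.2 tests no hypotheses and Section 6.5 reports no formal sample size calculation. An analysis plan could set counting rules, but the AE variables the protocol lists for collection do not carry the direction of change, so those rules would have to reconstruct it by matching entries. The correction therefore belongs in the protocol.

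**What to change.** In Section 4.7.1.2, replace *changes* with *worsens* (or *increases*), so that a new AE is recorded only when a pre-dose sign or symptom becomes more severe or becomes serious. This brings the rule into line with Section 4.7.1.1. Add that improvement or resolution is noted against the existing pre-dose entry and not opened as a new AE. Keep Visit 1 and recording from consent as they are.

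The cost is one amended sentence, one added sentence and a matching line in the CRF completion instructions. No visit, sample or assessment is added.

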4.7.1.3 Reporting of serious adverse events

Investigators and other site personnel must inform appropriate AstraZeneca representatives of any SAE that occurs in the course of the study within 1 day (i.e. immediately but no later than the end of the next business day) of when he or she becomes aware of it.

Follow-up information on SAEs must also be reported by the investigator within the same time frames.

If a non-serious AE becomes serious, this and other relevant follow-up information must also be provided to AstraZeneca within 1 day as described above. For a non-serious AE that become serious but which is not fatal or life-threatening a report should be received within 5 days.

The AstraZeneca representative will work with the investigator to compile all the necessary information and ensure that the appropriate AstraZeneca Drug Safety Department receives a report by day 1 for all fatal and life-threatening cases and by day 5 for all other SAEs.

All SAEs have to be reported, whether or not considered causally related to the investigational product or to the study procedure(s). All SAEs will be recorded in the pCRF. The investigator and/or Sponsor are responsible for informing the Ethics Committee and/or the Regulatory Authority of the SAE as per local requirements. For studies in countries implementing the EU Clinical Trials Directive, this will be taken care of by AstraZeneca (see Section 8.1).

4.7.2 Laboratory safety measurements and variables

4.7.2.1 Methods of assessment

1

Blood and urine samples for determination of clinical chemistry, haematology and urinalysis parameters, will be taken at the times given in the study plan (Table 1). The date of collection will be reported in \mathbb{T}^{M} .

Blood and urine collection for all safety parameters will be performed according to validated methods of AstraZeneca and Information for handling, labelling, storing and shipping will be provided in the laboratory handbook for safety blood and urine analyses.

The following laboratory variables for safety laboratory will be measured:

l	Clinical chemistry	Haematology
	P-Creatinine	B-Haemoglobin
	P-Total and unconjugated bilirubin-P- Total bilirubin	B-Leucocyte countB-Leucocyte count (absolute and differential)
	P-Alkaline phosphatase	B-Red cell count (RBC)
	P-Aspartate aminotransferase (AST)	B-Haematocrit
	P-Alanine aminotransferase (ALT)	B-Mean cell volume (MCV)
	P-Albumin	B-Mean cell haemoglobin (MCH)
	P-Potassium	B-Mean cell haemoglobin concentration (MCHC)
	P-Calcium, total	B-Platelet count
	P-Sodium	B-Reticulocyte count
	P-Cholesterol	
	P-Triglycerides	Urinalysis

41(59)

Clinical Study Protocol Drug Substance AZD9668 Study Code D0520C00002 Date	
P-Urea	U- Haemoglobin (RBC)
P-Gamma Glutamyltransferase (GGT)	U-Protein
P-Creatinine phosphokinase (CPK) ^b	U-Glucose
P-LDH	Pregnancy / FSH
P-Glucose (fasting)	βhCG / FSH as appropriate
P-Free thyroxine (T4) ^c	
P-Thyroid stimulating hormone (TSH) ^c	
P-Haptoglobin	
Virology ^d	

If elevated unconjugated bilirubin will be measured а

- b If elevated, P-CPK-MB will be analysed (will not be databased)
- с Included at Visit 1 only
- Hepatitis B and C and HIV status will be checked at Visit 1 only d

The respective laboratory reference ranges will be provided by the local laboratory and filed in the Investigator Site File (ISF).

These laboratory tests will be performed at the

using validated standard methods according to the applicable laboratory SOP. Laboratory data will be transmitted electronically from the to the study site.

4.7.2.2 Sputum for quantitative bacteriology

Spontaneous sputum samples for quantitative bacteriology will be taken at the times given in the study plan (Table 1). These will be performed according to the guidelines established at the local laboratory. Information for handling, labelling, storing and shipping of these sputum samples will be provided in the laboratory handbook.

4.7.2.24.7.2.3 Derivation or calculation of outcome variables

All individual values and changes to baseline of the laboratory parameters will be listed and summarized descriptively. Result of Virology and Drug screen including alcohol will only be listed.

Abnormal findings for laboratory variables should only be reported as AEs if they are accompanied by clinical symptoms, constitute SAEs or lead to discontinuation of treatment with the investigational product.

